1. INTRODUCTION AND BACKGROUND

Corneal transplantation has evolved rapidly in recent years. Lamellar keratoplasty to replace diseased endothelium has led to faster recovery times, fewer complications, and better visual acuity outcomes.¹ Currently, Descemet's Stripping Endothelial Keratoplasty (DSAEK) is the most common procedure because of its relative ease and good outcomes.² Newer techniques such as Descemet's Membrane Endothelial Keratoplasty (DMEK), where Descemet's membrane alone is transplanted, has the potential to further improve visual acuity outcomes, produce fewer higher-order corneal aberrations and decrease rejection rates.³⁻⁷ However, donor preparation, increased intra-operative times, and problems with donor attachment in DMEK are all important limitations.⁸⁻¹⁰

There are three potential mechanisms by which DMEK may provide better visual acuity outcomes than DSAEK: graft thickness, interface haze and corneal higher-order aberrations. Graft thickness has been correlated with best spectacle corrected visual acuity (BSCVA) outcomes among thinner grafts. One retrospective case series found that 71% of thin endothelial grafts (defined as <131 μ m) had BSCVA of 20/25 or better while only 50% of thick grafts (defined as \geq 131) achieved this.¹¹ In addition, higher-order aberrations, in particular of the posterior cornea, are increased after DSAEK. Theoretically, given the decreased tissue transplanted after DMEK this would be lessened; however, one retrospective series looking at higher order aberrations in DMEK compared with DSAEK found no difference in posterior aberrations of the central 4.0 mm zone between the two groups.¹⁰ Finally, interface haze may be increased in DSAEK and has been correlated with BSCVA.¹²

Ultrathin DSAEK involves donor preparation with a double microkeratome pass to produce donor grafts less than 100 um thick. This procedure may have similar results to DMEK but without the technical difficulties. Several large prospective series show similar visual outcome results and rates of immunologic rejection between ultrathin DSAEK and DMEK, however comparisons are difficult.^{11,13-15} This randomized controlled trial could directly address these important issues. We also anticipate that secondary analyses of the trial data will allow us to address several more.

Research Question: Are BSCVA outcomes, endothelial cell counts, and post-operative corneal light scatter and higher-order aberrations different between patients undergoing ultrathin DSAEK versus DMEK?

1.1 Specific Aims

- 1) **To determine whether there is a difference in best spectacle-corrected visual acuity (BSCVA) at 6 months between patients receiving ultrathin DSAEK and DMEK.** We hypothesize that the DMEK group will have improved visual acuity compared with DSAEK at 3 months, but not at 6 months. By randomizing 25 patients per arm, we anticipate 80% power to detect a one standard deviation, or approximately 1.2 Snellen lines, difference in BSCVA between the DMEK and DSAEK groups.
- 2) **To evaluate endothelial cell loss at 6 months between patients receiving ultrathin DSAEK and DMEK.** We hypothesize that there will be a difference in endothelial cell loss at 6 months between patients receiving ultrathin DSAEK and DMEK, accounting for pre-operative endothelial cell count.
- 3) **To assess the relative role of light scatter, higher-order aberrations and graft thickness on visual acuity.** We predict that there will be increased light scatter at the

graft-host interface and but no difference in posterior corneal higher-order aberrations of the central 4mm in DSAEK versus DMEK.¹⁰

While long-term outcomes such as graft rejection and survival are beyond the scope of the initial phase of this study, we anticipate we will be able to evaluate these as we follow patients at 12 and 24 months.

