3.4 Study Visits

3.4.1 Baseline Visit

During this visit, eligible patients who are enrolling for the first time will be enrolled in the study and will give consent. The baseline patient form will be completed and the NEI-VFQ will also be administered. If a patient includes a second eye in the study, they will complete an abbreviated baseline patient form for that study eye prior to surgery. They will not complete a second NEI-VFQ at the baseline visit for their second eye. Patients will also complete BSCVA, IOP, Pachymetry, and Pentacam tests at baseline.

3.4.2 *Surgery Visit*

The enrolled study participant's eye(s) will undergo either DSAEK or DMEK surgery. If both of a participant's eyes are included in the study, randomization to DSAEK or DMEK will be performed independently for each eye.

3.4.3 *Follow-Up Visits*

The follow-up patient form will be completed at each visit, for each enrolled eye. Data collected for each follow-up visit will include:

3 month follow-up: BSCVA, IOP, pentacam topography and densitometry pachymetry, optical coherence tomography, and endothelial imaging will be performed. The NEI-VFQ form will also be completed

6 month follow-up data: BSCVA, IOP, pentacam topography and densitometry pachymetry, optical coherence tomography, endothelial imaging, and slit-lamp photography will be performed.

12 month follow-up: BSCVA, IOP, pentacam topography and densitometry pachymetry, optical coherence tomography, and endothelial imaging will be performed. The NEI-VFQ form will also be completed

3.4.4 *Final Visit*

During the Month 24 final visit, the final status and follow-up patient forms will be completed. BSCVA, IOP, pentacam topography and densitometry pachymetry, optical coherence tomography, and endothelial imaging will also be performed.

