Descemet's Endothelial Thickness Comparison Trial

Statistical Analysis Plan

Francis I. Proctor Foundation, University of California San Francisco
Casey Eye Institute, Oregon Health & Science University
Byers Eye Institute, Stanford University

Investigators:

[name], PhD¹
[name], PhD*²
[name]*²
[name]*³
[name], COT²
[name], MS¹

*Principal Investigator

¹Casey Eye Institute, Oregon Health & Science University, Portland, Oregon

² Francis I. Proctor Foundation, University of California San Francisco, San Francisco, California

³Byers Eye Institute, Stanford University, Palo Alto, California

DETECT Statistical Analysis Plan

Table of Contents

1. Background	1
2. Sample Size and Randomization.....	1
3. Baseline Characteristics	1
4. Primary Analysis.....	1
5. Secondary Analyses	1
6. Other Data.....	2

1. Background

Descemets Endothelial Thickness Comparison Trial (DETECT) is a randomized, double-masked, two-arm clinical trial. The purpose of this study is to determine which of two types of corneal transplant surgeries has the better visual outcome. Study participant's eyes will be randomized to one of two treatment groups – 1.) Ultrathin Descemet's Stripping Endothelial Keratoplasty (DSAEK) or 2.) Descemet's Membrane Endothelial Keratoplasty (DMEK).

2. Sample Size and Randomization

We anticipate that 25 eyes per arm would provide 80% power to detect a 0.12 logMAR difference (approximately 1.2 Snellen lines), assuming two-tailed alpha, and a standard deviation of best spectacle-corrected visual acuity (BSCVA) at 6 months of 0.12 logMAR (approximately 1.2 Snellen lines) at 6 months. Participant's eyes will be randomized using random block sizes in Microsoft Excel ([name]).

3. Baseline Characteristics

Baseline characteristics between the 2 arms will be compared using Fisher exact test for categorical variables and Wilcoxon rank sum test for continuous variables.

4. Primary Analysis

For the primary study analysis, we will compare BSCVA between the two groups at the 6-month time period (between 5-7 months) using ANCOVA, with baseline BCVA and treatment group as covariates. Statistical significance will be assessed by permutation with a two-sided alpha of 0.05. (If the correlation coefficient between baseline BCVA and 6 month BCVA has magnitude less than 0.1, we will omit the variable entirely, yielding a post-test only analysis).

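### The protocol counts 25 patients per arm and the SAP 25 eyes per arm for the same 80% power, and that 80% does not follow from the stated inputs, which give about 93%

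*Protocol*

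**What the plan says.** **Sample size.** Protocol 1.1 (Specific Aims) states: "By randomizing 25 patients per arm, we anticipate 80% power to detect a one standard deviation". SAP section 2 states: "We anticipate that 25 eyes per arm would provide 80% power to detect a 0.12 logMAR difference", "assuming two-tailed alpha, and a standard deviation of best spectacle-corrected visual acuity (BSCVA) at 6 months of 0.12 logMAR". The number, the power and the effect (one SD, about 1.2 Snellen lines) agree. Only the unit differs. The SAP sentence names a two-tailed test but gives no alpha value there; SAP section 4 supplies it: "Statistical significance will be assessed by permutation with a two-sided alpha of 0.05".

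**Unit of randomisation and analysis.** Protocol 3.3 allocates each study eye. Protocol 3.4.2 says of participants with two study eyes that "randomization to DSAEK or DMEK will be performed independently for each eye". SAP section 4 includes every randomised eye in the 6-month intention-to-treat comparison. Protocol 3.4.1 provides a shortened baseline form for a second eye, and Protocol 6.2 counts visits per eye.

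**A conflicting sentence.** Protocol 4.2 limits each participant to a single operation. That does not fit a design in which both eyes may be enrolled.

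**The concern.** Two things look wrong in one statement.

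First, the unit. If every participant had one study eye, patients and eyes would be the same count. The design admits second eyes, so they are not. A participant whose two eyes are allocated differently belongs to both arms, and no rule says how that person counts towards 25 patients per arm.

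Second, the power. A one-SD difference is large, and 25 per arm is more than a conventional two-sample calculation needs for 80% power. Either the power is misstated or an assumption has been left out.

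At stake is whether a reader can reproduce the justification for the sample size and know what was counted. It also affects interpretation: readers will use the stated detectable difference when judging a null 6-month result, and 0.12 logMAR overstates the smallest difference that the trial can detect with 80% power.

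**Working it through.** **Inputs**
- n = 25 per arm, 1:1 (Protocol 1.1 and 1.3; SAP section 2)
- Difference δ = 0.12 logMAR and SD σ = 0.12 logMAR, so δ/σ = 1 (SAP section 2)
- Two-sided alpha 0.05 (SAP section 4)
- Stated power 80%

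**1. Try to reproduce the stated power.** Normal approximation:

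power = Φ(δ / (σ√(2/n)) − 1.96)

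√(2/25) = 0.2828, and 1/0.2828 = 3.536. Then 3.536 − 1.96 = 1.576, and Φ(1.576) = 94.2%. The noncentral t (48 degrees of freedom, noncentrality 3.536) gives 93.4%. The stated 80% is not reproduced; the gap is about 13 percentage points.

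**2. Sample size for 80%.** n = 2(1.96 + 0.842)²/(δ/σ)² = 2 × 7.85 = 15.7, so 16 per arm. The t version gives 16.7, so 17 per arm. Noncentral t power is 78.1% at 16 and 80.7% at 17.

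**3. Difference detectable with 80% power at 25 per arm.** Normal: 2.802 × 0.2828 = 0.79 SD, or 0.095 logMAR. Noncentral t: 0.809 SD × 0.12 = 0.097 logMAR.

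**4. What would give 80% at 25 per arm?**

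| Change to the inputs | Result | In the documents? |
|---|---|---|
| One-sided 0.05 (normal) | 97.1% | No; two-tailed is stated |
| Rank-test efficiency 0.864 (normal) | 90.8% | Ranks are a sensitivity analysis only |
| 25 eyes in total (12.5 per arm) | 67% (t) to 71% (normal) | No; 25 is per arm |
| Alpha 0.01 (t) | 79.9% | No; 0.05 is stated |
| 17 per arm inflated for 30% loss: 17/0.70 = 24.3 | 25 per arm | No loss rate is given |
| SD 0.148 logMAR: 0.12/0.809 | 80% | No; SD is 0.12 |

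The last three rows recover the figure, but each needs an assumption that neither document states. Adjusting for baseline acuity by ANCOVA would not bring power down towards 80%.

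**5. Does the choice of unit change the power?** Not if eyes are independent: 25 units per arm give the same result under either name. If fellow eyes are correlated (ρ), with c pairs in the same arm and d pairs split, the variance of the difference in means is

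σ²[2n + 2ρ(c − d)]/n²

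The documents give neither ρ nor the number of bilateral participants, so the values below are assumptions (normal approximation, 50 eyes).

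| Assumed case | All pairs same arm | Half split | All split |
|---|---|---|---|
| 12 of 38 participants bilateral, ρ = 0.5 | 88.8% | 94.2% | 98.2% |
| All 25 participants bilateral, ρ = 0.8 (limiting case) | 75% | 94.2% | near 100% |

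With eyes randomised independently, about half the pairs are expected to be split, so c − d is near zero and power stays near 94%.

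**The case against.** **The protocol plainly means eyes.** Protocol 3.3 and 3.4.2 randomise eyes, and Protocol section 8 sends the reader to the SAP for statistical detail. On this view the aims paragraph is loose wording for 25 randomised units per arm, and both documents intend 50 eyes. That is the most natural reading, and it is why the unit part is a correction of wording. It does not remove the inconsistency, because the protocol's only sample-size statement says patients, and the one-operation sentence in Protocol 4.2 supports a reader who takes it literally.

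**The two issues are separate.** This is true: the gap between 80% and 93% is the same whichever unit is used. They are taken together because they sit in the same sentence and one edit settles both.

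**The error is conservative.** This also stands. For independent eyes, 25 per arm exceeds the 17 needed, so the target is adequate for its stated aim.

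**A flat 93% would be another unqualified figure.** Fair. It holds only for independent eyes with no loss, so the restated figure must carry those assumptions. The documents do not require a cap on second eyes, and none is asked for here.

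**Conclusion.** The point holds as a unit inconsistency plus a power figure that its own inputs do not yield. For a 0.12 logMAR difference, SD 0.12, two-sided alpha 0.05 and 25 independent eyes per arm with none lost, power is about 93% (93.4% by noncentral t, 94.2% by normal approximation), not 80%. Equivalently, 80% power corresponds to about 0.097 logMAR.

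A reader might infer more than the documents support:

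- **That the protocol plans up to 100 eyes, with power near 100%.** This requires all 50 patients to be bilateral. No section plans or projects that.
- **That the two documents would close enrolment at different points.** Neither ties closure to these counts; the enrolment limit they state is the 24-month period.
- **That a count of patients per arm is meaningless.** It is well defined for participants with one study eye and fails only for those whose two eyes are split between arms.
- **That the trial is underpowered.** With independent eyes it has more power than stated. Power below 80% appears only under extreme assumptions, such as highly correlated fellow eyes that all fall in the same arm, and independent allocation makes that unlikely.

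**What to change.** 1. In Protocol 1.1, change the unit from patients to eyes, so that both documents state 25 eyes per arm (50 eyes).
2. In Protocol 1.1 and SAP section 2, either restate the power as about 93% for 0.12 logMAR (SD 0.12, two-sided alpha 0.05), or keep 80% and give about 0.097 logMAR as the detectable difference. Put the alpha value in the sample-size sentence, and say that the figure assumes independent eyes and no loss to follow-up.
3. If 25 per arm was meant to include an allowance for attrition, a stricter alpha or between-eye correlation, state the allowance and its value. For attrition, note that the SAP carries 3-month values forward, so only eyes with no follow-up data drop out of the analysis.
4. Reconcile Protocol 4.2 (one operation per participant) with Protocol 3.4.2 (both eyes may be enrolled).

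The cost is a few sentences in the protocol and SAP. No extra enrolment is needed.

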1.2 Study Outcomes

Primary Outcome:

- BSCVA at 6 months

Secondary Outcomes:

- Endothelial cell counts
- Corneal higher-order aberrations as measured by Pentacam
- Interface haze as measured by Pentacam densitometry
- Change in NEI-VFQ *from baseline to 3 months and 12 months*
- Primary graft failure, defined as a lack of graft clearing or need for re-graft within the first 2 months
- Graft rejection, defined as loss of graft clarity due to edema with evidence of inflammation such as anterior chamber cell or keratic precipitates.

Other Outcomes measured:

- Refraction
- Graft thickness as measured by OCT and pachymetry
- Operative times
- Adverse events/Complication rates

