As a methodological sensitivity analysis, we will conduct ANCOVA with ranks (which becomes the Wilcoxon rank sum test in the post-test only case). Model checking will be conducted for the primary analysis (and for all secondary analyses) based on analysis of residuals versus fitted values. We will conduct leave-one-out influence analysis to locate highly influential observations (a procedure we will apply to secondary analyses also). Individuals with missing six month data will be included based on last observation carried forward from the 3 month records; individuals with no follow-up data cannot be included but will be tabulated. Sensitivity analysis of missing values will be conducted to assess the range of values of missing observations that would be needed to change the results of the hypothesis test.

Protocol for measuring BCSVA is outlined in the MOP. BSCVA will be analyzed using an intent to treat analysis, with all eyes that are randomized being analyzed at 6 months regardless of subsequent surgery or graft failure. We will tabulate results by study site.

One safety analysis will be performed. No interim efficacy or futility analysis will be conducted.

5. Secondary Analyses

Key secondary outcomes

- We will analyze endothelial cell counts controlling for baseline endothelial cell count measured at the eye bank using mixed effect multiple linear regression conducted
- NEI-VFQ will be compared between the two groups with multiple linear regression, controlling for baseline VFQ.
- Three-month BCVA will be analysed using the same procedure as the primary outcome.
- A linear mixed model will be used in which both three and six month data are modeled, with a random intercept for eye, and with time, baseline BCVA, and treatment assignment as fixed effects. A graft rejection episode will be defined as loss of graft clarity due to edema with evidence of inflammation such as anterior chamber cell or keratic precipitates, and will be compared between the two groups using Fisher's exact test.
- For the purposes of this study, primary graft failure will be defined as a lack of graft clearing or need for re-graft within the first 2 months, and will be compared between the two groups using Fisher's exact test.

Supplementary secondary outcomes

- A pre-specified non-inferiority threshold is set at a 0.1 logMAR difference in visual acuity.

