- We will also look at BSCVA at using a last observation carried forward (LOCF) analysis. For study participants who experience primary graft failure and must undergo re-graft, graft failure will be noted and a BSCVA will be performed prior to performing further surgery. This last observation will be carried forward as the 6 month BSCVA.
- We will conduct the Kolmogorov-Smirnoff test to compare the 6-month (BSCVA) distribution between DMEK and DSAEK arms.
- Interface haze as measured by Pentacam densitometry will be analyzed using a Wilcoxon rank sum test.
- Corneal higher-order aberrations as measured by Pentacam will be analyzed using a Wilcoxon rank sum test.
- We will also perform a cost-effectiveness analysis of the clinical trial data, according to the protocol provided in the Supplementary Cost Effectiveness Analysis Statistical Analysis Plan.

6. Other Data

Other data to be collected include manifest refraction, graft thickness as measured by OCT, pachymetry, operative times, and adverse events or complications.

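### Aim 3 asks how haze, aberrations and graft thickness bear on acuity, but no acuity analysis in the SAP includes any of the three

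*Protocol*

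**What the plan says.** Aim 3 in Protocol 1.1 opens with "To assess the relative role of light scatter, higher-order aberrations and graft thickness on visual acuity". It then makes two between-arm predictions: more scatter at the interface after DSAEK, and no difference in posterior aberrations within the central 4 mm. Protocol 1 gives the motive: "There are three potential mechanisms by which DMEK may provide better visual acuity outcomes than DSAEK: graft thickness, interface haze and corneal higher-order aberrations". Protocol 8 contains no analysis of its own and refers to the SAP.

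In SAP 4 the primary comparison of 6-month BSCVA is made "using ANCOVA, with baseline BCVA and treatment group as covariates". In SAP 5 the mixed model for 3- and 6-month acuity is fitted "with time, baseline BCVA, and treatment assignment as fixed effects". On the factors themselves, SAP 5 says "Interface haze as measured by Pentacam densitometry will be analyzed using a Wilcoxon rank sum test" and "Corneal higher-order aberrations as measured by Pentacam will be analyzed using a Wilcoxon rank sum test". Graft thickness is among the other outcomes in Protocol 1.2 ("Graft thickness as measured by OCT and pachymetry"). SAP 6 lists it only as something to collect: "Other data to be collected include manifest refraction, graft thickness as measured by OCT".

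**The concern.** The lead sentence of Aim 3 treats acuity as the outcome and the three factors as explanatory variables. An analysis that answers it must have acuity on one side and the factors on the other, and the SAP contains none. A test of whether haze differs between arms says nothing about how haze relates to acuity.

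At stake is a secondary aim, not the primary comparison. If the aim is reported anyway, several choices would be made after the data are seen: whether arm is in the model, which visit supplies the optical measurements, how carried-forward acuity and re-grafted eyes are handled, and how two eyes of one patient are treated. The choice about arm could alter the answer for graft thickness, because thickness differs greatly between the two procedures.

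**Working it through.** **Step 1: the acuity analyses set against Aim 3.** The plan gives no figure for Aim 3, so there is none to reproduce. Light scatter is read here as interface haze by Pentacam densitometry, an inference that favours the plan.

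| SAP acuity analysis | Terms used | Any Aim 3 factor? |
|---|---|---|
| Primary ANCOVA (SAP 4) | arm, baseline acuity | no |
| ANCOVA on ranks (SAP 4) | same | no |
| Missing-value sensitivity; site tabulation (SAP 4) | no added covariate | no |
| 3-month acuity (SAP 5) | as primary | no |
| Mixed model, 3 and 6 months (SAP 5) | time, arm, baseline acuity | no |
| Non-inferiority margin (SAP 5) | margin only | no |
| LOCF version (SAP 5) | changes the imputed value only | no |
| Kolmogorov-Smirnov (SAP 5) | arm only | no |

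The count with any Aim 3 factor is 0. Haze and aberrations appear only as outcomes compared by arm. Thickness is not compared even by arm.

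**Step 2: what an Aim 3 regression could detect.** SAP 2 plans 25 eyes per arm, 50 in all. For 80% power at two-sided 0.05, the detectable partial correlation is tanh[(1.960 + 0.842)/√(n − 3 − k)], with k the number of other covariates. With three factors, arm and baseline acuity in the model, k = 4 for each factor.

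- n = 50: tanh(2.802/√43) = 0.40
- n = 45: tanh(2.802/√38) = 0.43
- n = 40: tanh(2.802/√33) = 0.45
- DSAEK only (no arm term, k = 3): n = 25 gives tanh(2.802/√19) = 0.57; n = 20 gives tanh(2.802/√14) = 0.63

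At an observed partial correlation of 0.3, the Fisher-z 95% CI is 0.01 to 0.54 (50 eyes), −0.03 to 0.57 (40 eyes) and −0.14 to 0.64 (25 DSAEK eyes).

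These figures treat eyes as independent. For a patient with two study eyes under a random intercept, information relative to two independent eyes is (1 − ρc)/(1 − ρ²), with ρ the residual and c the predictor correlation within a patient. It is 0.90 at ρ = 0.3, c = 0.6 and 1.33 at ρ = 0.5, c = 0. The documents give neither, so the direction is unknown.

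**Step 3: can thickness be in the pooled model with arm?** Protocol 4.2.1 gives DSAEK grafts of about 60 to 90 microns. If uniform, the variance is 30²/12 = 75. DMEK thickness is not in the documents; assume 10 (SD 3), 20 (SD 3) or 30 (SD 5) microns. With arm in the model only within-arm variation counts, so the DMEK mean drops out. Assume a common slope, equal residual variance, and haze, aberrations and baseline acuity unrelated to thickness within arm.

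- DSAEK only: 24 × 75 × (21/24) = 1575
- Pooled, DMEK SD 3: (24 × 75 + 24 × 9) × (45/48) = 1890; SE ratio √(1575/1890) = 0.91
- Pooled, DMEK SD 5: (24 × 75 + 24 × 25) × (45/48) = 2250; SE ratio √(1575/2250) = 0.84

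Simulation gave 0.91, 0.91 and 0.83 for the three settings. The pooled thickness SE is thus about 0.83 to 0.91 of the DSAEK-only SE.

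**Step 4: optional baseline adjustment of aberrations.** Simulation: 40,000 trials per setting, 25 independent eyes per arm, assumed shift 0.82 SD, assumed baseline correlation r. Power is for Wilcoxon against rank ANCOVA with the SAP's rule of omitting the baseline when the correlation is below 0.1.

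| r | Wilcoxon | Rank ANCOVA with rule |
|---|---|---|
| 0 | 78.0% | 77.7% |
| 0.1 | 78.4% | 78.5% |
| 0.3 | 78.5% | 81.6% |
| 0.5 | 78.2% | 87.7% |

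Type I error with the rule was 5.0% throughout. The 95% CI half-width, t × √(2/25) × √(1 − r²) SD, is 0.57 SD unadjusted, 0.54 at r = 0.3 and 0.49 at r = 0.5.

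**The case against.** The best defence is that the Research Question in Protocol 1 asks only whether scatter and aberrations differ between arms. Aim 3's two explicit predictions are also between-arm, and the SAP tests both. Thickness ranks only as an other outcome, the introduction anticipates further secondary analyses, and the trial is small for a multi-factor regression. Much of this stands. It keeps the gap well below the primary comparison and makes rewording one sentence a complete cure. It does not remove the gap: the introduction's remark specifies no model, and Aim 3 is a numbered aim. The separate documents in Protocol 10.2 are, by title, measurement and eye bank protocols, and the supplementary SAP concerns cost-effectiveness. Their contents were not available.

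Two stronger readings are tempting.

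- A reader might infer that thickness cannot be separated from arm, so that only a DSAEK-only model could compare all three factors. Under the assumed DMEK thicknesses arm does explain about 91 to 96% of thickness variance, a variance inflation that multiplies the SE by 3.3 to 5.1. But that multiplier compares with a hypothetical predictor of the same total variance unrelated to arm. It does not compare with the DSAEK-only model, against which the pooled model is the more precise.
- A reader might infer that the unadjusted Wilcoxon test on aberrations is an error. It is valid. The gain from adjustment depends on a correlation the documents do not give, and it may be small because both operations replace posterior tissue. Nor is the surface or zone shown to be undefined: the separate Pentacam Protocol may state it.

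**Conclusion.** The point holds as an omission in a secondary aim, of minor to moderate weight. No planned acuity analysis contains haze, aberrations or thickness, and thickness is not analysed at all. This is a textual finding that rests on no assumption beyond reading light scatter as interface haze. The primary result and both Wilcoxon tests remain valid.

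The remedy has limits. A partial correlation of about 0.40 is detectable with 50 eyes treated as independent, and smaller associations would be left with wide intervals. The thickness precision figures rest on assumed DMEK thicknesses and a common within-arm slope. A reader might expect the regression to show why one procedure does better; it gives associations only and cannot do so.

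**What to change.** 1. **Aim 3.** Choose one of two options.
   - Reword Aim 3 to the between-arm comparisons that are planned.
   - Or pre-specify one exploratory regression of observed 6-month BSCVA on same-visit posterior aberrations (central 4 mm), densitometry and graft thickness together. Adjust for arm and baseline BSCVA, allow for two eyes of one patient, and report standardised coefficients with 95% CIs. Do not carry 3-month acuity forward into this model. List re-grafted and excluded eyes by arm. Give a DSAEK-only model solely as a sensitivity check on the common slope; with about 25 eyes a patient random intercept may not be estimable. State that these are imprecise associations that do not explain an arm difference.
2. **Optional efficiency gain.** State the visit for both Pentacam tests. Analyse 6-month aberrations by the SAP's own rank ANCOVA with the eye's pre-operative value, omitted if the correlation is below 0.1 in magnitude, and give an adjusted difference with 95% CI. The cost is one degree of freedom and a rule for missing baseline scans, such as the pooled median of both arms. Expect no gain at a correlation of 0 to 0.1.
3. **Interface haze.** Keep the Wilcoxon test, since there is no graft interface before surgery.

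The cost is one reworded sentence, or some SAP text and one further model with its sensitivity check. Protocol 4.4 already schedules acuity, Pentacam and OCT at month 6 and Pentacam pre-operatively, so no new visit or test is needed.
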